8.2 Data collection

Designated investigator staff will enter the data required by the protocol into the OC/RDC system. Designated investigator site staff will not be given access to the system until they have been trained.

Automatic validation procedures within the system check for data discrepancies during and after data entry and, by generating appropriate error messages, allow the data to be confirmed or corrected online by the designated investigator site staff. The Investigator must certify that the data entered into the electronic Case Report Forms are complete and accurate. After database lock, the investigator will receive copies of the patient data for archiving at the investigational site.

Adapted ACR Pediatric response and disease flare occurrence will be determined centrally from data (ACR components) provided by the investigator. These will be derived and communicated to the investigator the same day.

8.3 Database management and quality control

Novartis staff review the data entered into the CRFs by investigational staff for completeness and accuracy and instruct the site personnel to make any required corrections or additions. Queries are sent to the investigational site using an electronic data query. Designated Investigator site staff is required to respond to the query and confirm or correct the data.

Concomitant medications entered into the database will be coded using the World Health Organization (WHO) Drug Reference List, which employs the Anatomical Therapeutic Chemical classification system. Concomitant procedures, non-drug therapies and adverse events will be coded using the Medical dictionary for regulatory activities (MedDRA) terminology.

Laboratory samples (except for CRP) will be processed centrally and the results will be sent electronically to Novartis (or a designated CRO).

ECG readings will be processed centrally and the results will be sent electronically to Novartis (or a designated CRO).

Randomization codes and data about all study drug(s) dispensed to the patient and all dosage changes will be tracked using an Interactive Response Technology (IRT). The system will be supplied by a vendor, who will also manage the database. The database will be sent electronically to Novartis (or a designated CRO).

Each occurrence of a code break via IRT will be reported to the clinical team and monitor. The code break functionality will remain available until study shut down or upon request of Novartis.

The occurrence of relevant protocol deviations will be determined. After these actions have been completed and the database has been declared to be complete and accurate, it will be locked and the treatment codes will be unblinded and made available for data analysis. Any changes to the database after that time can only be made after written agreement by Novartis Development management.

8.4 Data Monitoring Committee

An independent external data monitoring committee (DMC) will be appointed to monitor the safety of the study subjects.

The DMC will periodically review patient disposition and safety data throughout the study as specified in the DMC Charter to ensure the safety of the patients. The DMC will be composed of external individuals with experience and expertise in the management of pediatric patients, including those with autoimmune conditions.

An independent statistician and statistical programmer will prepare the information for the DMC. Members of the DMC will not share any unblinded or partially-blinded information with anyone outside of the DMC. The Sponsor will remain fully blinded to any results throughout the study unless the DMC recommends changes in the conduct of the study (for example, early termination due to negative safety findings).

Details regarding the DMC process, responsibilities and membership will be described in the DMC charter.

8.5 Adjudication Committee

Not required.

9 Data analysis

A general description of the statistical methods to be used to analyze the efficacy and safety data is outlined below. Specific details will be provided in the Statistical Analysis Plan.

This trial is conducted as a three-part study. Data summaries may be presented separately for each study part and for combined study parts where appropriate.

Unless otherwise stated, all statistical tests will be two-sided at the 5% significance level and accompanied by two-sided 95% confidence intervals where appropriate.

Any data analysis carried out independently by the Investigator should be submitted to Novartis before publication or presentation.

The trial follows the recommendation of the Consolidated Standards of Reporting Trials (CONSORT) statement and results are reported for the intention-to-treat population ([Schulz et al 2010](#)).

9.1 Analysis sets

The following analysis sets will be used in this trial:

The randomized set will be defined as all subjects who were randomized in Treatment Period 2. Unless otherwise specified, mis-randomized subjects (mis-randomized in IRT) will be excluded from the randomized set.

Mis-randomized subjects are defined as those subjects who were mistakenly randomized into the IRT prior to the site confirming all eligibility criteria had been met and to whom no study medication was given in Treatment Period 2.

The Full Analysis Set (FAS) Treatment Period 2 will consist of all randomized patients who received at least one dose of study drug in Treatment Period 2. Following the intent-to-treat principle, patients will be analyzed according to the treatment they were assigned to at randomization in Treatment Period 2.

The FAS Treatment Period 1 will consist of all patients who received at least one dose of study drug in Treatment Period 1.

The FAS Treatment Period 3 will consist of all patients who received at least one dose of study drug in Treatment Period 3. Following the intent-to-treat principle, patients will be analyzed according to the treatment they were assigned to at randomization in Treatment Period 2.

The Safety Set for a treatment period will consist of all patients that received at least one dose of study drug in that treatment period. Patients will be analyzed according to treatment received. Of note, the statement that a patient had no adverse events also constitutes a safety assessment.

9.2 Patient demographics and other baseline characteristics

Demographics and baseline characteristics

Demographic and baseline characteristics will be summarized descriptively for the FAS for Treatment Period 1 and Treatment Period 2 by treatment group and overall. Continuous variables will be summarized by mean, standard deviation, median, minimum, maximum, 25% and 75% quantiles, and number of patients with non-missing data. Categorical variables will be summarized by absolute frequencies and percentages.

Comparability of treatment groups in Treatment Period 2 with respect to the demographic and baseline characteristics will be assessed descriptively.

Relevant medical history/current medical conditions will be listed and summarized by system organ class and preferred term of the MedDRA dictionary.

9.3 Treatments

Study treatment

The exposure to study drug (number of injections) and duration of exposure (days) will be summarized and listed.

The number and percentage of patients taking medication and non-drug therapies will be summarized by preferred term according to the WHO Drug Reference List dictionary (which employs the Anatomical Therapeutic Chemical classification system). Separate summaries will be provided for therapies that ended prior to Treatment Period 1 (prior therapies) and were active after the start of Treatment Period 1 (concomitant therapies).

The FAS corresponding to the study periods summarized will be used.

9.4 Analysis of the primary variable(s)

9.4.1 Variable(s)

The primary efficacy endpoint will be time to disease flare event in Treatment Period 2, which is defined as the interval between the date of randomization to the date of first occurrence of disease flare event. The analysis of the primary efficacy endpoint will be based on the FAS Treatment Period 2.

All subjects who enter Treatment Period 2 will be followed until the sooner of either experiencing a disease flare or the end of Treatment Period 2 when 33 flare events are observed. Subjects who have not experienced flare event at the end of Treatment Period 2 data (as defined in [Section 3.1](#)) or discontinue prematurely from Treatment Period 2 before it closes for reasons other than experiencing a disease flare will be censored at the date of the last efficacy evaluation in Treatment Period 2.

Statistical model, hypothesis, and method of analysis

The primary objective for Treatment Period 2 of the study is to show superiority of secukinumab over placebo regarding the primary variable in Treatment Period 2.

The following statistical hypothesis will be tested once the required number of flares has been observed and the study has been stopped:

$$H_0: 1 - S_{AIN}(t) \geq 1 - S_{Pla}(t)$$

$$H_A: 1 - S_{AIN}(t) < 1 - S_{Pla}(t)$$

at each time point t , with $S_{AIN}(t)$ and $S_{Pla}(t)$ being the survivor functions in the secukinumab and placebo treatment group at time t .

The two treatment groups will be compared using a one-sided stratified Logrank test with the stratification factor of JIA category (ERA or JPsA) at the 2.5% level of significance. Hazard ratios and their associated 95% confidence intervals will be estimated based on a Cox proportional hazards model with treatment and stratification factor as explanatory variables.

The Kaplan-Meier estimates of the proportion of patients with the flare event at selected landmark points, along with its 95% confidence intervals using Greenwood's formula, will be provided. The primary analysis will be based on the FAS for Treatment Period 2.

Handling of missing values/censoring/discontinuations

All patients in Treatment Period 2 will have a value of time to flare either by having an event or being censored.

Supportive analyses

For sensitivity purposes, the primary analysis will be repeated using an unstratified log-rank test.

The primary analysis will be repeated where patients discontinuing the study for any reason will be considered as having flare at the time of study discontinuation.

Subgroup analyses for the primary efficacy variable will be performed for stratification factor: JIA category (ERA or JPsA).

Analysis of secondary variables

9.4.2 Efficacy variables

[figure not shown]
The analysis of secondary variables is descriptive only for FAS. Summary statistics will be presented. Summary statistics for continuous variables include N, mean, standard deviation, minimum, median, maximum, 25% and 75% quantiles, and number of patients with non-missing data. For binary or discrete variables the number of subjects in each category and relative frequencies will be provided.

The following secondary efficacy endpoints will be analyzed for all patients and each JIA category by descriptive statistics in Treatment Period 1:

- JIA ACR 30/50/70/90/100 and inactive disease status
- Each JIA ACR core component
- Change from baseline Juvenile Arthritis Disease Activity Score (JADAS) score
- Total enthesitis count
- Total dactylitis count

The following secondary efficacy endpoints will be analyzed for all patients and each JIA category by descriptive statistics in Treatment Period 2, and/or other periods, as appropriate:

- JIA ACR 30/50/70/90/100 and inactive disease status

9.4.4 Safety variables

The analysis of safety data may be provided for each Treatment Period separately and all periods combined, as appropriate. The analysis of safety data will be conducted on the Safety Set, which includes subjects who receive any study treatment and have at least one post-baseline safety assessment. All data will be analyzed according to the treatment actually received.

The safety variables to be analyzed include Adverse events (AEs), clinical laboratory tests (hematology and chemistry), physical examination results, ECGs, and deaths. Safety variables are to be tabulated by descriptive statistics (n, mean, median, standard deviation, minimum, and maximum; or n and percent). No formal statistical testing is planned.

9.4.4.1 Adverse events

Adverse events will be coded using the MedDRA dictionary that provides the primary system organ class and preferred term information. Adverse events will be presented in two parts:

- Adverse events (including infections)
- Infectious adverse events

Adverse events will be summarized by presenting, for each study period and each treatment group, the number and percentage of patients having any adverse event, having any adverse event in each primary system organ class and having each individual adverse event based on the preferred term. All other information collected (e.g. severity, relationship to study drug) will be tabulated and listed as appropriate.

Deaths, serious adverse events, and adverse events leading to discontinuation of study drug will be summarized by primary system organ class and preferred term and listed.

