Treatment Period 3: Patients experiencing a disease flare in Treatment Period 2 will immediately enter Treatment Period 3 to receive open label secukinumab every 4 weeks until total study duration of 104 weeks for that patient is achieved. Additionally, when Treatment Period 2 closes, all remaining patients in Treatment Period 2 will enter Treatment Period 3 at their next scheduled visit and all remaining Treatment Period 1 patients who become eligible to enter Treatment Period 2 will skip Treatment Period 2 and enter Treatment Period 3 directly. Consequently, the starting time point of Treatment Period 3 for each patient may be different.

Post-treatment follow-up: All patients completing the study (Week 104) or who discontinue early will enter the Post-treatment follow-up period lasting 12 weeks from the last study drug dose administration. Only patients who qualify and enter the secukinumab extension trial without interruption of secukinumab treatment will not require this Post-treatment follow-up visit.

Due to the event driven design of Treatment Period 2, the lengths of Treatment Periods 2 and 3 will be variable and patient-specific. Based on the study design, a patient may participate in:

1. **Treatment Period 1 only** if the patient is a non-responder at the end of Treatment Period 1 and must discontinue from the study.
2. **Treatment Periods 1, 2, and 3.**
3. **Treatment Periods 1 and 2 only** if the patient never experiences a disease flare after randomization into Treatment Period 2 and reaches a total study duration of 104 weeks before a total 33 flares in Treatment Period 2 are observed.
4. **Treatment Periods 1 and 3 only** if 33 flares are observed in Treatment Period 2 prior to or at the time the patient reaches Week12 (end of Treatment Period 1) and is eligible to enter Treatment Period 2. In this situation, the patient will enter Treatment Period 3 directly from Treatment Period 1 to receive open-label secukinumab.

All patients will participate in the Post-treatment follow up period, except for those entering the extension study.

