3.6 Risks and benefits

Secukinumab has shown efficacy in several inflammatory diseases, including PsA, AS, and psoriasis. The large safety dataset of secukinumab cross-indication did not show unexpected safety issues relative to the known mode of action. In general, secukinumab is safe and well-tolerated and has demonstrated a similar safety profile to other mAbs (including etanercept and ustekinumab). The most frequently reported AEs are non-serious infections, especially upper respiratory tract infections. In addition, there is an increase in mucosal or cutaneous candidiasis with secukinumab compared with placebo, but the cases were generally mild or moderate in severity, non-serious, and responsive to standard treatment. There is also a small increase in neutropenia cases with secukinumab compared with placebo. Common Terminology Criteria for adverse event (CTCAE) grade 3 neutropenia ($<1.0-0.5 \times 10^9/L$) was uncommonly observed with secukinumab, most were mild to moderate, transient and reversible, and without a temporal relationship to serious infections. Hypersensitivity reactions include urticaria. Rare events of anaphylactic reaction to secukinumab have also been observed in clinical studies.

The immunogenicity potential, e.g. eliciting the production of anti-drug antibodies (ADA) is low. In psoriasis, psoriatic arthritis and ankylosing spondylitis clinical studies, less than 1% of patients treated with secukinumab (n>9600) developed antibodies over up to 52 weeks of treatment.

Taking into account the individual risks as outlined above, the expected risk profile of secukinumab from its mechanism of action is anticipated to be similar or improved compared to the other approved inflammatory cytokine-targeting therapies. The risk to subjects in this trial will be minimized by compliance with the eligibility criteria, close clinical monitoring, and extensive guidance to the investigators provided by Novartis and in the current version of the Investigator Brochure (IB) for Secukinumab. Based on overall risk-benefit assessment, the current trial with secukinumab is justified.

4 Population

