7.1 Adverse events

An adverse event (AE) is any untoward medical occurrence (e.g., any unfavorable and unintended sign, including abnormal laboratory findings, symptom or disease) in a subject or clinical investigation subject *after providing written informed consent* for participation in the study until the end of study visit. Therefore, an AE may or may not be temporally or causally associated with the use of a medicinal (investigational) product.

In addition, all reports of intentional misuse and abuse of the product are also considered an adverse event irrespective if a clinical event has occurred.

The occurrence of adverse events must be sought by non-directive questioning of the patient at each visit during the study. Adverse events also may be detected when they are volunteered by the patient during or between visits or through physical examination findings, laboratory test findings, or other assessments.

Abnormal laboratory values or test results constitute adverse events only if they fulfill at least one of the following criteria:

- they induce clinical signs or symptoms,
- they are considered clinically significant,
- they require therapy.

Clinically significant abnormal laboratory values or test results must be identified through a review of values outside of normal ranges/clinically notable ranges, significant changes from Baseline or the previous visit, or values which are considered to be non-typical in patient with underlying disease. Investigators have the responsibility for managing the safety of individual patient and identifying adverse events. Alert ranges for laboratory and other test abnormalities are included in [Appendix 1](#).

Adverse events must be recorded in the Adverse Events CRF page under the signs, symptoms or diagnosis associated with them, accompanied by the following information:

- the severity grade
 - mild: usually transient in nature and generally not interfering with normal activities
 - moderate: sufficiently discomforting to interfere with normal activities
 - severe: prevents normal activities
- its relationship to the study treatment (no/yes), or other treatment (no/yes), or both, or indistinguishable

- its duration (start and end dates) or if the event is ongoing an outcome of not recovered/not resolved must be reported.
- whether it constitutes a serious adverse event (see [Section 7.2.1](#) for definition of SAE)
- action taken regarding investigational treatment

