9.6 Sample size calculation

It is assumed that the Flare-free time follows an exponential distribution with a constant hazard ratio.

The hazard ratio of flare events for the secukinumab group relative to placebo group is estimated to be 0.32 in Treatment Period 2. The hazard ratio of 0.32 was used to establish the sample size necessary in Treatment Period 2 and consequently Treatment Period 1 (derived from the median time to disease flare for ETANERCEPT and placebo in LOVELL et. al. 2000). With the hazard ratio assumed to be 0.32, 33 flares are necessary to detect a statistically significant difference between secukinumab and placebo assuming 90% power and a 1-sided significance level of 0.025. No data is available to estimate the placebo hazard rate beyond 6-months. Given that uncertainty and a maximum 21-month follow-up in Treatment Period 2, the total sample size necessary to achieve 33 flares in Treatment Period 2

is estimated to be at least 60 and at most 80 patients. Assuming approximately 70% to 85% of patients respond in Treatment Period 1, the estimated minimum number of patients treated in Treatment Period 1 is between 70 and 86. Under the assumption of 12 months of accrual duration, the total maximum expected study duration is 33 months. The expected number of flare events is 12 and 21 respectively for secukinumab and placebo group in Treatment Period 2.

10 Ethical considerations

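### Crude percentages of patients with adverse events in Treatment Period 2 ignore that placebo time is cut short by flare, so infections and other non-flare events are expected to look more frequent on secukinumab at equal true risk

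*Protocol*

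**What the plan says.** Section 9.4.4.1 sets the adverse event display: "for each study period and each treatment group, the number and percentage of patients having any adverse event", then the same by system organ class and preferred term. All adverse events form one part and infectious events another. Section 9.4.4 applies the same rule to categorical safety variables in general (n and percent) and plans no formal testing. Section 9.1 defines the Safety Set per treatment period as everyone dosed in that period, so the denominator is the same however long a patient was observed.

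Time in Treatment Period 2 depends on the efficacy outcome. Under section 9.4.1 patients "will be followed until the sooner of either experiencing a disease flare or the end of Treatment Period 2". Section 3.1 adds: "Patients experiencing a disease flare in Treatment Period 2 will immediately enter Treatment Period 3", where treatment is open-label secukinumab. Section 9.6 states the expected effect: "The hazard ratio of flare events for the secukinumab group relative to placebo group is estimated to be 0.32 in Treatment Period 2".

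Exposure appears only in section 9.3: "The exposure to study drug (number of injections) and duration of exposure (days) will be summarized and listed". Nothing in the protocol relates adverse event counts to time at risk. Section 9.4.4.3 speaks of incidence rates, but only for notable laboratory abnormalities and without a person-time definition.

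**The concern.** A percentage of patients with an event compares two arms fairly when both are observed for about the same time. Here unequal observation is a planned result of the design: the more secukinumab delays flare, the shorter the placebo follow-up, and the less chance a placebo patient has of contributing an infection to the Treatment Period 2 table.

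Treatment Period 2 is the only randomised, placebo-controlled part, so its tables are the only randomised safety comparison. Section 3.6 says of secukinumab: "The most frequently reported AEs are non-serious infections, especially upper respiratory tract infections". It also reports more candidiasis and neutropenia than on placebo. The artefact points the same way, so a reader of the crude tables could not separate real risk from longer observation.

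**Working it through.** **Inputs from the protocol.** Hazard ratio 0.32, exponential flare-free time, 33 flares, 90% power, one-sided 0.025, 60 to 80 patients in Treatment Period 2, 12 months of accrual, at most 21 months of follow-up, 12 and 21 expected flares (section 9.6); 1:1 allocation (section 5.3); four-weekly visits, at most 92 weeks in the period, closure at the 33rd flare, later responders skip the period (section 3.1).

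**Assumptions not in the protocol.** Event rate r of 0.1, 0.5 or 1.0 per patient-year, equal in both arms and unrelated to flare; placebo median time to flare of 2 to 12 months; no dropout.

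**The plan's own figure.** Schoenfeld: 4 × (1.960 + 1.282)² / (ln 0.32)² = 32.4, rounded up to 33, with power 90.5%. The stated 33 is reproduced.

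**Closed-form check.** Take 30 patients per arm and 21 months of follow-up for all, and choose the hazards so that 33 flares are expected at a hazard ratio of 0.32. This gives h = 0.0652 per month on placebo and 0.0208 on secukinumab.

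- Mean time in the period is (1 − exp(−21h))/h: 11.4 months on placebo and 17.0 on secukinumab, ratio 1.49.
- The chance of a first event in the period is r/(r+h) × [1 − exp(−21(r+h))]. At 0.5 per patient-year, r = 0.0417 per month:
  - placebo 0.390 × 0.894 = 34.9%;
  - secukinumab 0.667 × 0.731 = 48.7%.
- Mean time to first event or end of period is [1 − exp(−21(r+h))]/(r+h): 8.37 months on placebo and 11.70 on secukinumab. First events per patient-year are then 0.349 × 12/8.37 = 0.50 and 0.487 × 12/11.70 = 0.50. The rate recovers equality where the percentage shows a gap of 13.8 points.

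This form was repeated for 60 and 80 patients, for follow-up of 21 months or uniform over 9 to 21 months, for calibration to a hazard ratio of 0.32 or to the 12/21 split, and for rates of 0.1 to 2. The time ratio was 1.19 to 1.51. The crude percentage was higher on secukinumab in all 40 settings, by 1.6 to 17.4 points.

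**Simulation of the design.** Patients accrue uniformly over 12 months. Flares are detected at four-weekly visits, the period closes at the 33rd flare, remaining patients leave at their next visit, and later entrants skip the period. There were 3000 runs per setting, with N = 60, 70 or 80. Crude incidence is the mean of 1 − exp(−r × time in period).

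| Hazard ratio | Time ratio | Excess at 0.1 | Excess at 0.5 | Excess at 1.0 |
|---|---|---|---|---|
| 0.32 | 1.30–1.66 | 1.1–3.7 | 4.8–12.4 | 8.1–15.7 |
| 0.5 | 1.19–1.38 | 0.7–2.3 | 3.0–7.8 | 5.0–9.9 |
| 0.7 | 1.09–1.19 | 0.3–1.1 | 1.4–4.0 | 2.4–5.2 |

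Excess is secukinumab minus placebo, in percentage points. For example, with N = 60 and a placebo median of 8 months at 0.32, mean time is 13.5 against 9.1 months and crude incidence at 0.5 per patient-year is 41.2% against 29.6%. The exposure-adjusted rate ratio at 1.0 per patient-year is 0.98 to 1.02 throughout.

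At 0.32 the secukinumab percentage is strictly higher in 48–61% of trials at rate 0.1 (where the excess is 0.4 to 1.1 patients per arm), 70–81% at 0.5 and 76–88% at 1.0.

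**If flares are recorded as adverse events.** Section 7.1 defines an adverse event broadly ("any unfavorable and unintended sign, including abnormal laboratory findings, symptom or disease"), and the text does not exclude a JIA flare. With a share f of flares recorded, incidence is the mean of 1 − exp(−r × time) × (1 − f × flare). At 0.32 and rate 1.0, the difference in the row of any adverse event is +1.3 to +9.8 points for f = 25% and −5.6 to +4.0 for f = 50%. It vanishes at f between 30% and 69% (rate 1.0) or between 17% and 43% (rate 0.5).

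**The case against.** The strongest objection is that this belongs in the SAP. Section 9 calls itself a general description and refers specifics to that document, which could add rates without contradicting the protocol. Counts and percentages are also correct as descriptions. This would succeed against a complaint that something is missing. The point here is that the protocol states a measure, and that measure fits a design in which follow-up ends at the efficacy event badly.

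A second objection concerns size. Simulated settings close to the protocol's 12 and 21 flares (N = 60 or 70, placebo median 2 months) give only 1.2–1.4, 5.3–5.9 and 8.9–9.8 points at the three rates. The top of the range comes from N = 60 with medians of about 8 to 12 months, and the 33rd flare is reached in only 68% of runs at a median of 10 and 32% at 12. It is fair that the smaller figures match the expected split best. However, restricting to settings that reach 33 flares in at least 97% of runs still gives up to 3.3, 11.7 and 15.6 points, so the upper values do not depend on settings in which the event target is missed.

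Several limits stand. For rare terms the shift is close to noise. The row of any adverse event can go either way. All randomised patients first had 12 weeks of secukinumab, so early placebo time is not clean control time under either measure. No test is affected, and the tilt overstates rather than hides risk.

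**Conclusion.** The concern holds for infections and other events unrelated to flare. The direction requires only a flare hazard ratio below 1, which the trial is planned on; with no effect on flare there would be no tilt. The size rests on assumed event rates and placebo medians: at the planning hazard ratio, roughly 1 to 4 points for events at 0.1 per patient-year and 5 to 16 points for those at 0.5 to 1.0. The higher percentage on secukinumab is expected, not certain, in any one trial. The exposure summary in section 9.3 shows the imbalance but does not correct any percentage. This is a worthwhile, low-cost improvement to a descriptive display and leaves the trial's inference untouched.

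**What to change.** In section 9.4.4.1, for Treatment Period 2 and for any table that combines periods, keep n (%) and add exposure-adjusted incidence rates: patients with a first event per 100 patient-years at risk, with 95% confidence intervals, by treatment received. Base any description of differences between the arms on these rates.

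Two smaller clarifications would help the reader:

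- State whether JIA flare terms count in the row of any adverse event and, if they do, show that row with and without them.
- Footnote that early placebo time follows 12 weeks of open-label secukinumab.

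The cost is a sentence or two of wording and a few standard tables, since exposure duration is already derived under section 9.3. The rates assume a constant hazard, do not remove carry-over of secukinumab into early placebo time, and will have wide intervals for rare preferred terms.
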